# 1 SYNOPSIS

NAME OF COMPANY Sanofi Genzyme [name]
 
NAME OF FINISHED PRODUCT Fabrazyme
 
NAME OF ACTIVE INGREDIENT agalsidase beta
	
SUMMARY TABLE Referring to Part..... of the Dossier:  Volume: Page:  Reference:
	
FOR NATIONAL AUTHORITY USE ONLY:

TITLE: A Multicenter, Multinational Study of the Effects of Fabrazyme® (agalsidase beta) Treatment on Lactation and Infants
		

PROTOCOL NO.: AGAL02603 / MSC12868
		

INVESTIGATOR/STUDY CENTERS: Investigators at approximately 10 multinational study centers will participate.
		

OBJECTIVES: The objectives of this study are:
 
 
1. To determine whether αGAL (alpha-galactosidase A) activity is present in the breast milk of mothers with Fabry disease who are being treated with Fabrazyme during lactation.
 
2. To measure breast milk production and composition (volume, protein and fat content) in women with Fabry disease who receive Fabrazyme during lactation.
 
3. To determine whether Fabrazyme affects the growth, development, and immunologic response of infants born to mothers with Fabry disease who receive Fabrazyme during lactation.
 
		

METHODOLOGY: This is a multicenter, multinational study of the potential effects of Fabrazyme on lactation and on the growth, development, and immunologic response of infants born to mothers with Fabry disease who are treated with Fabrazyme during lactation. Pregnant women who received Fabrazyme at any point during their pregnancy can be enrolled in the study. If woman is not receiving treatment with Fabrazyme at the Baseline visit, mother should start treatment with Fabrazyme between the delivery and Month 1 visit.
 
Mother: Breast milk will be collected at Months 1, 3, and 6 immediately prior to Fabrazyme infusion, just after the end of the infusion, and 2 hours after the end of the infusion. Breast milk samples will be analyzed for volume, presence of αGAL activity, total fat content, and total protein concentration. Blood samples from the mother will be drawn for pharmacokinetic (PK) analysis prior to each breast milk collection. Lactation status, adverse events (AEs), and concomitant medications will be collected at every visit. If infant genotyping is performed on the umbilical blood cord sample at Baseline visit, a buccal cell sample will be obtained from the mother to rule out contamination of the cord blood sample with maternal DNA (deoxyribonucleic acid) (maternal cell contamination (MCC) analysis). The following data items will be collected through the Registry: medical history (including Fabrazyme status during pregnancy), pregnancy outcome, serum immunoglobulin G (IgG) antibodies, and genotyping.
 
Infant: If the parent(s)/legal guardian(s) consents to infant participation, the infant's growth and development will be assessed at Months 1, 2, 3, and 6, then at 6-month intervals through Month 24. The infant may also be tested for the formation or continued presence of IgG (immunoglobulin G) and IgM (immunoglobulin M) antibodies to recombinant human α galactosidase A (r-hαGAL) at Baseline, Months 2, 6, and 12 and for genotype at Baseline.
		

NUMBER OF SUBJECTS: Mothers: Approximately 10 mothers and up to 10 infants will be enrolled in this study.
		

NAME OF COMPANY Sanofi Genzyme [name]
 
NAME OF FINISHED PRODUCT Fabrazyme
 
NAME OF ACTIVE INGREDIENT agalsidase beta
	
SUMMARY TABLE Referring to Part..... of the Dossier: Volume: Page: Reference:
	
FOR NATIONAL AUTHORITY USE ONLY:


DIAGNOSIS/INCLUSION-EXCLUSION CRITERIA:
 
Inclusion Criteria - Mothers must meet the following criteria to be enrolled in this study:
 
 
I 01. provide signed written informed consent to participate in this study,
 
I 02. be enrolled in the Fabry Registry and receiving Fabrazyme while lactating,
 
I 03. agree to adhere to the Fabry Registry recommended schedule of assessments for medical history, pregnancy outcome, genotyping, and antibody testing, and
 
I 04. agree to adhere to the schedule of evaluations for this study.
 
 
Inclusion Criteria - Infants must meet the following criteria to be enrolled in this study:
 
 
I 05. have the signed written informed consent of the parent(s)/legal guardian(s) to participate in this study,
 
I 06. be born to a mother who is receiving Fabrazyme during lactation,
 
I 07. be receiving breast milk from the mother, and
 
I 08. have the agreement of the parent(s)/legal guardian(s) to adhere to the schedule of evaluations for this study.
 
 
Exclusion Criteria The mother and infant will be excluded from this study if the mother has received an investigational drug within 30 days prior to study enrollment.
		

DOSE/ROUTE/REGIMEN: Mothers receive Fabrazyme treatment (commercially available) at their prescribed dose and regimen as determined by their treating physician.
		

REFERENCE TREATMENT: No reference treatment will be used in this study.
		

NAME OF COMPANY Sanofi Genzyme [name]
 
NAME OF FINISHED PRODUCT Fabrazyme
 
NAME OF ACTIVE INGREDIENT agalsidase beta
	
SUMMARY TABLE Referring to Part..... of the Dossier:
 
Volume: Page:
 
Reference:
	
FOR NATIONAL AUTHORITY USE ONLY:


CRITERIA FOR EVALUATION:
 
Mother
 
 
• Efficacy: Efficacy will not be measured in this study.
 
• Pharmacokinetics: Blood and breast milk samples will be taken from the mother at Months 1, 3, and 6 for measurement of αGAL concentrations (if mother is lactating at the time of the evaluation and is receiving Fabrazyme therapy). Blood samples will be collected prior to each breast milk collection as follows: sample 1: immediately prior to Fabrazyme infusion and prior to breast milk collection; sample 2: just prior to the end of Fabrazyme infusion and prior to breast milk collection; and sample 3: 2 hours after Fabrazyme infusion and prior to breast milk collection. Breast milk samples will be collected after each plasma collection for PK testing as follows: sample 1: immediately prior to Fabrazyme infusion and after plasma collection; sample 2: immediately after Fabrazyme infusion and after plasma collection; and sample 3: 2 hours after Fabrazyme infusion and after plasma collection. The volume of breast milk expressed from each timepoint (immediately prior to infusion, from infusion start until end of infusion, and from end of infusion until 2 hours post-infusion) will be recorded and summarized.
 
• Breast Milk: Samples of expressed breast milk will be collected by pump at Months 1, 3, and 6 (if mother is lactating at the time of the evaluation and continues to receive Fabrazyme therapy) for PK assessment as above. Additionally, the volume, fat content, and protein content of breast milk samples will be determined.
 
• Safety: The IgG antibody titers and incidence of adverse events (AEs) occurring in mothers enrolled in this study will be summarized.
 
 
Infant
 
 
• Efficacy: Efficacy will not be measured in this study.
 
• Immunoglobulins: At birth, a sample of umbilical cord blood will be collected to determine the infant's Baseline anti-r-hαGAL IgM and IgG titers. Testing for presence of IgG and IgM antibodies will also occur at Month 2, 6, and 12.
 
• Development: The infant's growth and development will be monitored from birth to Month 24 through physical exams and the Denver II Developmental Screening Test.
 
• Safety: The incidence of adverse events occurring in infants enrolled in this study will be summarized.
 
 
Genotype testing: will be conducted for all participating infants on umbilical cord blood to determine diagnosis of Fabry disease. In cases when umbilical blood cord sample is not collected at the Baseline visit, genotyping of the infant enrolled for full participation could be performed on the additional blood sample collected at visit month 12. If genotyping of the infant is performed as a part of standard care prior to visit month 12, this result will be recorded by Investigator in the CRF (Case Report Form).
		


NAME OF COMPANY Sanofi Genzyme [name]
 
NAME OF FINISHED PRODUCT Fabrazyme
 
NAME OF ACTIVE INGREDIENT agalsidase beta
	
SUMMARY TABLE Referring to Part..... of the Dossier: Volume: Page: Reference:
	
FOR NATIONAL AUTHORITY USE ONLY:


STATISTICAL AND ANALYTICAL PLANS:
 
Statistical Methods: Data collected in this study will be analyzed using descriptive statistics and reported using summary tables, graphs, figures, and/or patient data listings. No hypothesis testing will be performed. Details of the statistical analysis will be specified in the Statistical Analysis Plan.
 
Study Variables
 
Mother: The following study variables from the mothers will be summarized:
 
 
● Plasma αGAL activity
 
● Milk αGAL to plasma αGAL ratio;
 
● The levels of αGAL activity, volume, total fat and protein content in breast milk samples;
 
● Lactation status;
 
● Frequency of AEs, coded using the Medical Dictionary for Regulatory Activities (MedDRA);
 
● Concomitant medications received.
 
 
Each lactating woman will serve as her own control, with pre-infusion and post-infusion breast milk samples. The following data will be collected through the Registry and summarized:
 
 
● Medical history (including Fabrazyme status during pregnancy);
 
● Genotyping;
 
● Pregnancy outcomes;
 
● IgG antibody.
 
 
Infant: The following study variables from the infants will be summarized:
 
 
● Medical history;
 
● Physical exam;
 
● Gender;
 
● Apgar scores at 1 minute and 5 minutes after birth;
 
● Denver II Developmental Screening Test;
 
● IgM antibody titer to r-hαGAL;
 
● IgG antibody titer to r-hαGAL;
 
● Genotype;
 
● Frequency of AEs, coded using MedDRA;
 
● Concomitant medications received.
 
 
Sample Size: No formal statistical sample size calculations were performed for this study. The sample size of approximately 10 mothers and up to 10 infants is based upon 1) the availability of mothers to study lactation in this rare disease and 2) the availability of infants whose parents or legal guardians consent to their participation in this study.
 
Interim Analysis: After 5 mothers have contributed breast milk samples to this study, an interim analysis of αGAL activity in the breast milk will be performed. [REDACTED]
 
In addition, status of this study will be summarized annually as part of the Fabry Registry Program Annual Report.
		

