#### **9.4.7 Breast Milk Samples**

Breast milk samples of mothers receiving Fabrazyme will be tested for  $\alpha$ GAL activity, volume, and fat and protein content. Since  $\alpha$ GAL is a protein, it is a normal component of breast milk and it is possible that the women enrolled in the study naturally produce  $\alpha$ GAL in the breast milk samples. The current assay cannot differentiate between endogenous  $\alpha$ GAL and Fabrazyme. As breast milk samples are not available prior to the mother having started Fabrazyme therapy, breast milk samples will be tested just prior to the Fabrazyme infusion and at timed intervals as specified above (see [Section 9.3](#)) to see if there is an increase in the  $\alpha$ GAL levels in breast milk.

Each breast milk collection should first be measured for total volume. An aliquot of each breast milk sample collected at the site is to be set aside for testing and the remainder of the sample may be fed to the infant. Refer to the SOM for further details on breast milk sampling.

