## 11.10 PHARMACOKINETICS ANALYSIS

Because of the limited sampling schedule, the only PK parameters that will be reported are maximum concentration ( $C_{max}$ ) and area under the plasma  $\alpha$ GAL concentration-time curve (AUC) from 0 to 2 hours post end of infusion ( $AUC_{0-2}$ ). A more complete PK profile is not being done because it is not the objective of the study to characterize the pharmacokinetics of  $\alpha$ GAL in lactating mothers.

Lactation clearance will be determined using the same calculations used to assess renal clearance. Breast milk will be collected at Baseline (sample 1) to empty each breast of milk, at end of infusion (sample 2), and 2 hours post-dose (sample 3). The amount of  $\alpha$ GAL will be calculated as the product of  $\alpha$ GAL activity times the milk volume. AUC from Baseline to 2 hours after the end of infusion will be calculated using a linear trapezoid. Lactation clearance will be estimated as the amount of  $\alpha$ GAL excreted over the sampling period divided by the AUC during the sampling period. The milk to plasma ratio calculated as the  $AUC_{milk}$  to  $AUC_{plasma}$  from time 0 (sample 2) to 2 hours after the end of infusion (sample 3) will also be computed.

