1.2 OBJECTIVES

1.2.1 Primary objectives

The primary objectives of this study are:

1. To determine whether α GAL activity is present in the breast milk of mothers with Fabry disease who are being treated with Fabrazyme during lactation.
2. To measure breast milk production and composition (volume, protein and fat content) in women with Fabry disease who receive Fabrazyme during lactation.
3. To determine whether Fabrazyme affects the growth, development, and immunologic response of infants born to mothers with Fabry disease who receive Fabrazyme during lactation.

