2.1.4 Safety endpoints

The safety analysis will be based on the reported adverse events (AEs) and other safety information, such as physical examinations, etc.

The following study variables will be summarized as appropriate for the mothers (items marked with * will be collected through the Registry):

- Medical history (including Fabrazyme status during pregnancy)*
- Genotyping*
- Pregnancy outcome*
- IgG antibody status*
- Lactation status
- Plasma and breast milk PK testing
- The level of α GAL, volume, and fat and protein content in breast milk samples
- Frequency of AEs
- Frequency of concomitant medications

The following study variables will be summarized as appropriate for the infants:

- Medical history
- Physical examination
- Gender

- Genotype
- Apgar score at 1 minute and 5 minutes after birth
- Denver II Developmental Screening Test
- IgM antibodies to r-hαGAL – presence, time to development, level of titers present
- IgG antibodies to r-hαGAL – presence, time to development, level of titers present
- Frequency of AEs
- Frequency of concomitant medications

Observation period

The on-study observation period is defined as the time from the signing of the informed consent until the end of the study (defined as last protocol planned patient contact by telephone approximately 28 days after the final study procedures are completed).

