2.4.5.6 Analyses of other safety endpoints

2.4.6 Analyses of pharmacokinetic and pharmacodynamic variables

Descriptive statistics of pharmacokinetic (PK) parameters by visit and by mother and infant groups will be provided. However, in case of sparse data, a by patient listing will be provided.

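### Milk production is a primary objective in the SAP, but volume is summarised only per collection; sample 2 spans an infusion of unstated length and no rate is planned

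*Protocol*

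**What the plan says.** SAP 1.2.1 names as a primary objective "To measure breast milk production and composition (volume, protein and fat content) in women with Fabry disease who receive Fabrazyme during lactation". Protocol section 5 has the same objective, unranked.

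Volume then appears as follows:

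- Protocol synopsis, Criteria for Evaluation (Mother): the volume expressed immediately before infusion, and "from infusion start until end of infusion, and from end of infusion until 2 hours post-infusion) will be recorded and summarized".
- Protocol 9.4.7: "Each breast milk collection should first be measured for total volume".
- SAP 2.1.4 lists the αGAL level, "volume, and fat and protein content in breast milk samples", to be summarised as appropriate, with no time unit. Protocol 11.8 does the same.
- Protocol 9.3 and 11.10 and SAP 2.1.5 use volume to obtain the amount of αGAL in milk and, from that, lactation clearance. That is a clearance of enzyme, not a rate of milk production.

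Neither document gives an infusion rate or duration. The regimen is left to the treating physician and preparation to country labeling (Protocol 6.2.1 and 8.1). Emptying of the breast is stated for sample 1 only (Protocol 11.10): "Breast milk will be collected at Baseline (sample 1) to empty each breast of milk, at end of infusion (sample 2", with sample 3 two hours later. The synopsis lists volume among the mothers' study variables and, after that list, says each woman is her own control through pre- and post-infusion samples.

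**The concern.** A volume measures production only relative to the time over which the milk accumulated. The three collections differ in this respect. Sample 3 covers a nominal 2 hours. Sample 2 covers the infusion, whose length is not given. Sample 1 has no defined start, because the plan does not ask for the time since the breast was last emptied.

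A reader comparing sample 2 volumes between visits or mothers could therefore take a difference in infusion length for a difference in production, or miss a real change that infusion length offsets. If the own-control statement in the synopsis is meant to cover volume, the pre-against-post contrast has no interpretable scale at all. In a study of about 10 mothers with no hypothesis testing, the descriptive summaries are the result, so the summarised quantity ought to represent the objective.

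**Working it through.** The plan has no figure on this point to reproduce.

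**From the documents:** the sample 3 interval is 2 h, and sample 1 is intended to empty the breast.

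**Assumed:** infusion length T of 4, 3 or 2 h; constant secretion of 1 unit per hour; no drug effect.

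1. **Full emptying at each collection.** Sample 2 volume S2 = T and sample 3 volume S3 = 2.
   - S2 ratio for 4 h to 3 h: 3/4 = 0.75. For 4 h to 2 h: 2/4 = 0.50.
   - S2/T = 1 in every case, so the mL/h ratio is 1.00.
   - Masking: a true 25% fall with an infusion lengthening from 3 h to 4 h gives 0.75 × 4/3 = 1.00 on raw volume.

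2. **Incomplete emptying.** Let f be the fraction removed at each collection and t the hours between an earlier complete emptying and sample 1. Then R1 = (1−f)t; S2 = f(R1+T); R2 = (1−f)(R1+T); S3 = f(R2+2); combined rate C = (S2+S3)/(T+2). Take f = 0.8 or 0.9, the same at both visits, and t = 1, 2 or 3 h, free to differ between visits. The extremes occur at f = 0.8:

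| Visit | S2 | S2 per h | S3 | C |
|---|---|---|---|---|
| T=4, t=1 | 0.8×4.2 = 3.36 | 0.84 | 0.8×2.84 = 2.272 | 5.632/6 = 0.939 |
| T=2, t=3 | 0.8×2.6 = 2.08 | 1.04 | 0.8×2.52 = 2.016 | 4.096/4 = 1.024 |
| T=4, t=3 | 0.8×4.6 = 3.68 | 0.92 | 0.8×2.92 = 2.336 | 6.016/6 = 1.003 |
| T=2, t=1 | 0.8×2.2 = 1.76 | 0.88 | 0.8×2.44 = 1.952 | 3.712/4 = 0.928 |

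   Ratios for 4 h to 2 h, where the truth is 1.00:
   - raw S2: 1.76/3.68 = 0.48 to 2.08/3.36 = 0.62
   - S2 in mL/h: 0.88/0.92 = 0.96 to 1.04/0.84 = 1.24
   - combined rate: 0.928/1.003 = 0.93 to 1.024/0.939 = 1.09

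3. **Sensitivity of the range.** If t is equal at both visits, the combined rate is 0.99-1.02 and S2 in mL/h is 1.02-1.13, but nothing in the plan fixes t. If f also differs, the low end widens slightly. With f = 0.9, t = 3, T = 4: S2 = 0.9×4.3 = 3.87, S3 = 0.9×2.43 = 2.187, C = 6.057/6 = 1.010. Against f = 0.8, t = 1, T = 2, the ratios are 1.76/3.87 = 0.45 (raw), 0.88/0.9675 = 0.91 (mL/h) and 0.928/1.010 = 0.92 (combined).

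4. **Sample 3 against sample 2 within one visit, T = 4.** With f = 0.8 and t = 3, the ratio is 1.168/0.92 = 1.27 in mL/h and 2.336/3.68 = 0.63 raw. Over f = 0.8-0.9 and t = 1-3 h it is 1.13-1.35 in mL/h and 0.57-0.68 raw. Neither scale supports a between-sample contrast under incomplete emptying.

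**The case against.** The objective itself names volume as the measure of production, and the plan delivers volume with each interval labelled. Nothing in the documents shows that infusion lengths differ. By-visit statistics are promised for PK parameters (SAP 2.4.6), not expressly for volume, and with fewer than 5 mothers only listings are produced (SAP 2.4). Infusion data are listed (SAP 2.4.3.1), so a reader might be able to check. The incomplete-emptying model is also open to challenge: the 80-90% has no source in the documents, and it is applied to sample 1 although Protocol 11.10 intends that collection to empty the breast.

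This limits the size and certainty of the point but does not remove it. A labelled interval of unknown length still does not give production, and a listing contains a rate only if someone derives it. The halving in step 1 does not use the disputed model.

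Two stronger readings are tempting. A reader might infer that a pre-against-post volume contrast is definitely planned. The synopsis wording is ambiguous and does not settle it either way. A reader might also infer from "2.4.5.6 Analyses of other safety endpoints", which stands without text, that volume will not be analysed. Volume is listed for summary elsewhere, and text may have been lost in extraction, so that heading carries no weight here.

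**Conclusion.** The gap is real and modest. Production is a primary objective in the SAP, sample 2 volume mixes production with infusion length, and no rate is planned. At constant production with full emptying, 4 h to 2 h gives a ratio of 0.50 on raw volume and 1.00 in mL/h. Under the assumed incomplete emptying (same fraction at both visits), raw volume gives 0.48-0.62, sample 2 mL/h 0.96-1.24 and the combined rate 0.93-1.09. The combined rate is therefore clearly better than raw volume when infusion length changes, but not exact. The tighter 0.99-1.02 should not be claimed for it, because that needs equal time since last emptying at both visits.

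A reader might infer that this trial's volume results are in fact distorted. The documents do not show that, because infusion lengths are not given. Nor would a rate allow a volume finding to be credited to Fabrazyme. Protocol 9.4.7 says "As breast milk samples are not available prior to the mother having started Fabrazyme therapy", and Protocol 11.1 rules out hypothesis testing. The consequence is for descriptive interpretation only.

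**What to change.** In SAP 2.1.4, and wherever milk volume is summarised:

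- Keep raw volume for the enzyme amount and lactation clearance.
- Report the actual interval length and mL/h for samples 2 and 3, and one combined rate per visit: (sample 2 + sample 3 volume) / hours from sample 1 to sample 3. Put the same items in the listings if data are sparse.
- State that single-sample rates assume the breast is emptied at each collection and that no milk is taken in between.
- Do not contrast volume or rate between samples, including pre against post, unless emptying and time since last emptying are known. Say whether the own-control statement in the synopsis is meant to cover volume.
- Label these summaries as descriptive and not attributable to Fabrazyme.

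The cost is a few SAP sentences and a little programming, with no extra samples and no change to how infusions are given. The AUC in Protocol 11.10, from Baseline to 2 hours after the infusion, already needs elapsed times, so a rate is probably derivable from planned data. A time field would be needed only if those times are not recorded. That cannot be checked, because the CRF and the Study Operations Manual are not among the documents.

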### 3 LIST OF ABBREVIATIONS

AE:	adverse event
AUC:	area under the concentration-time curve
CHO:	Chinese Hamster Ovary
C max :	maximum concentration
CRF:	case report form
DNA:	deoxyribonucleic acid
GCP:	Good Clinical Practice
GL-3:	globotriasylceramide
HEENT:	head, ears, eyes, nose, and throat
IAR:	infusion-associated reactions
ICH:	International Conference on Harmonization
IEC:	independent ethics committee
IgG:	Immunoglobulin G
IgM:	Immunoglobulin M
IRB:	institutional review board
MCC:	Maternal Cell Contamination
MedDRA:	Medical Dictionary for Regulatory Activities
PK:	pharmacokinetics
q2w:	every two weeks
r-hαGAL:	recombinant human alpha galactosidase A
SAE:	serious adverse event
SOM:	Study Operations Manual
SOP:	Standard Operating Procedure
US:	United States
αGAL:	alpha-galactosidase A

